7.6. Urodynamics Assessments (Urodynamics Sub-study Only)

Urodynamics assessments are collected at or within 6 months prior to Baseline and at Week 12 for Part 2 subjects who consented to participate in the Urodynamics sub-study. Urodynamics parameter estimates will be assessed by a central reviewer. The following parameters will be measured:

- Peak flow rate during voiding (Qmax) (mL/s)
- Detrusor pressure at peak flow rate (Corrected PdetQmax) (cmH₂O)
- Instilled volume at first involuntary detrusor contraction (IDC) (Vol@1st IDC) (mL), if an IDC occurs
- Maximum detrusor pressure during the first involuntary detrusor contraction (Corrected Pdet@1st IDC) (cmH₂O), if an IDC occurs
- Maximum cystometric capacity (Corrected MCC) (mL)
- Maximum detrusor pressure during the storage phase (Corrected PdetQmax Storage) (cmH₂O)
- Voided volume (VV) (mL)

Additional parameters will be derived from the measured values:

- Bladder Outlet Obstruction Index (BOOI)= $P_{det}Q_{max}-2\cdot Q_{max}$
- Bladder Contractility Index (BCI)= $P_{det}Q_{max} + 5\cdot Q_{max}$
- Bladder Voiding Efficiency (BVE)=($VV\cdot 100$)/MCC

Descriptive statistics of observed values at Baseline, Week 12, any time post-baseline, and change from baseline to Week 12 and to any time post-baseline will be presented for each of the parameters for the UES set. Least squares mean estimates and 95% CIs as described in section 4.2.2 will be presented from an ANCOVA model including terms for treatment and baseline parameter value. One-sided 95% CIs will be provided for Q_{max} and $P_{det}Q_{max}$.

Categorical summaries of BOOI [Unobstructed (<20), Equivocal (20-40), and Obstructed (>40)] and BCI [Strong (>150), Normal (100-150), Weak (<100)] will also be presented.

If PP-UES differs from UES by more than 5 subjects, Q_{max} and $P_{det}Q_{max}$ will be summarized as above for the PP-UES population.

All urodynamics assessments will be listed, including investigator derived parameters. If a urodynamics measurement was taken after the end of study date in URO-901-3005 (implying that the subject initiated URO-901-3006 before the evaluation), that measurement will not be included in any tabular summaries but will be listed.

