9.4.3.4. Urodynamics

Descriptive statistics of observed values at Baseline and Week 12, and the change from baseline at Week 12 for the following urodynamic parameters will be presented for each treatment group by visit:

- Instilled volume at first involuntary detrusor contraction (Vol@1st IDC) (mL)
- Corrected maximum detrusor pressure during the first involuntary detrusor contraction (P_{det}@1st IDC) (cmH₂O)
- Corrected maximum cystometric capacity (MCC) (mL)
- Corrected maximum detrusor pressure during the storage phase (P_{det}@Max Storage) (cmH₂O)
- Peak flow rate during voiding (Q_{Max}) (mL/s)

- Corrected detrusor pressure at peak flow rate ($P_{det}@Q_{Max}$) (cmH₂O)
- Voided volume (VV) (mL)

This analysis will only apply to the sub-study in Part 2.

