3.1.5. Urodyamics Evaluable Set

The Urodynamics Evaluable Set (UES) consists of all subjects in Part 2 who were randomized to the urodynamics sub-study, received at least one dose of double-blind study medication, had both Qmax and PdetQmax measurements at baseline and at least one Qmax or PdetQmax measurement at the post-baseline timepoint.

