4.2.3. Premature Withdrawal and Missing Data

All data collected in the study database after the subject’s cessation of study treatment should be included in summary and analysis. Data of subjects who withdraw after the screening examination or are not treated will only be listed. Assessments taken after the End of Study visit date for subjects continuing on to study URO-901-3006 will not be included in analysis or listings for study URO-901-3005; it will be included in datasets to support inclusion in analysis of study URO-901-3006.

If any visits are missing diary data, no explicit missing data imputation will be performed for the primary analysis of change from baseline since a mixed model for repeated measures (MMRM) will be applied to change from baseline analysis. If time to bed or time to awaken the next morning is missing from a diary day, the average of non-missing days for that subject at that visit

will be used. If no visit average bedtime or time of awakening is calculable, no nocturia measurements will be calculated for that subject at that visit.

Missing items from the subject reported outcomes (PROs) will be handled according to the respective measure instructions as described in Section 4.3.2.

Missing return dates from the study drug log will be imputed as the day of the subsequent drug dispensation, end of treatment visit, or subject discontinuation in the study, whichever is first. Non-return of IP will be considered taken per protocol for calculation of treatment compliance but will be noted in the listing of study medication.

If the first dose of double-blind study medication is not witnessed, the start of medication will be imputed as the day after the drug was dispensed.

In general, missing safety data will not be imputed and only observed values will be analyzed.

If the relationship of an AE record (“Relationship to investigational product” on AE CRF) is missing this AE will be considered “Probably Related” to the study treatment. If the AE intensity is missing every effort should be made to acquire the information from the investigator. “Severe” will be assigned to a missing intensity for reporting purposes.

The general imputation rules of partial missing date and time for both AE and concomitant medication is detailed below:

Dates missing the day of the year will adhere to the following conventions:

- The missing day of onset date will be set to:

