4.3.4. Baseline and Change from Baseline

In general, the last recorded value on or prior to the date of randomization will serve as the baseline measurement for efficacy endpoints while the last recorded value prior to first double-blind dose of study treatment will serve as the baseline measurement for safety endpoints. The mean of multiple values will be used as baseline for the following situations:

- If multiple measurements are scheduled on the same baseline day (i.e., blood pressure)
- If multiple measurements are collected on the same baseline day without the time or “repeat” status to differentiate the records

For efficacy endpoints derived from the Bladder Diary, the baseline will be the average value over the diary days in the baseline analysis visit window.

Change from baseline will be calculated as the post-baseline value minus the baseline value. Percentage change from baseline will be calculated as the change from baseline divided by the baseline value, multiplied by 100. If either the baseline or post-baseline value is missing, then change from baseline and percentage change from baseline will be set to missing.

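### The planned change and ANCOVA comparisons of volume and pressure at first involuntary detrusor contraction (IDC) keep only men with an IDC at both visits, so they are not randomised comparisons

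*SAP*

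**What the plan says.** SAP 7.6 lists seven measured parameters for the urodynamics sub-study. Two are conditional: "Instilled volume at first involuntary detrusor contraction (IDC) (Vol@1st IDC) (mL), if an IDC occurs", and "Maximum detrusor pressure during the first involuntary detrusor contraction", which carries the same condition. Protocol 8.3.7 states the condition too. Protocol 9.4.3.4 names the volume only as "Instilled volume at first involuntary detrusor contraction", leaves the condition out, and plans descriptive statistics alone.

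For each parameter in the Urodynamics Evaluable Set (UES), SAP 7.6 plans "Descriptive statistics of observed values at Baseline, Week 12, any time post-baseline, and change from baseline to Week 12". It then adds least squares means with 95% confidence intervals "from an ANCOVA model including terms for treatment and baseline parameter value". No parameter is exempted. The model code in SAP 4.2.2, to which 7.6 refers, takes change from baseline as the response and requests the difference between treatments.

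Two general rules decide what happens to a man without an IDC:
- SAP 4.2.3: "In general, missing safety data will not be imputed and only observed values will be analyzed".
- SAP 4.3.4: "If either the baseline or post-baseline value is missing, then change from baseline and percentage change from baseline will be set to missing".

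The UES itself does not depend on IDCs. It takes dosed sub-study men who "had both Qmax and PdetQmax measurements at baseline and at least one Qmax or PdetQmax measurement at the post-baseline timepoint" (SAP 3.1.5).

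Neither document says how to treat a completed test without an IDC. The only categorical summaries in SAP 7.6 are of the obstruction and contractility indices.

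**The concern.** A test that shows no IDC is a result, not a missing measurement. The plan gives it the same status as a test that was never done.

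The loss is foreseeable. The background in Protocol 2.3.1 describes this drug class as relaxing bladder smooth muscle and suppressing detrusor instability in rodent models. If vibegron stops IDCs in some men, those men drop out of the two comparisons because of their response. The men left in each arm are then selected by an outcome of treatment, and randomisation no longer makes the arms comparable. Protocol 9.4.4.1 gives the aim of the urodynamic analysis as assessing vibegron's effect on these parameters, and a model-based estimate with a confidence interval invites that reading.

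**Working it through.** **1. The plan's own figures.** The only power figures for the sub-study are in SAP 1.2.4.2: 30 evaluable men per arm, one-sided 0.05, margins 3 mL/s and 15 cmH2O, SDs 3.2 and 23.5. Power = Φ(margin / (SD × √(2/30)) − 1.645).
- Qmax: 3 / (3.2 × 0.2582) = 3.631; Φ(1.986) = 97.6% (stated 97%).
- PdetQmax: 15 / (23.5 × 0.2582) = 2.472; Φ(0.827) = 79.6% (stated 79%).
- Both: 0.9765 × 0.796 = 77.7% (stated 77%). Enrolment: 60 / (1 − 0.20) = 75, as stated.

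These reproduce. None concerns an IDC parameter, and the point below does not change them.

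**2. Who has a change value.** For men tested at both visits:

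| IDC at Baseline | IDC at Week 12 | Change value | In the ANCOVA |
|---|---|---|---|
| yes | yes | yes | yes |
| yes | no | missing (4.3.4) | no |
| no | yes | missing (4.3.4) | no |
| no | no | missing | no |

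Requiring an IDC at Baseline only defines a subgroup fixed before randomisation. Requiring one at Week 12 as well conditions on an outcome after randomisation. The summary of any post-baseline value does not normally bring these men back, because only one post-baseline test is scheduled.

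**3. How many are analysed.** The documents give no IDC rates, so these are assumptions. Number per arm = 30 × P(IDC at Baseline) × (1 − P(IDC lost)). Baseline rates of 40%, 60% and 80% are shown.
- Placebo, 10% lost: 10.8, 16.2, 21.6.
- Vibegron, 10% lost: the same. With 30% lost: 8.4, 12.6, 16.8. With 50% lost: 6.0, 9.0, 12.0.

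**4. Direction of the bias.** The planned ANCOVA was simulated with 400,000 men per scenario. It was compared, in men with a baseline IDC, with an analysis that keeps lost IDCs (volume set to capacity, pressure set to 0) and, where the model has one, with the underlying effect. All inputs are assumed.

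| Scenario | IDC lost, placebo / vibegron | As planned | Lost IDCs kept | Underlying effect |
|---|---|---|---|---|
| Volume: loss unrelated to threshold, others shift 20 mL | 10% / 20% | 16.8 mL | 22.1 mL | – |
| Same | 10% / 30% | 16.5 mL | 28.6 mL | – |
| Same | 10% / 50% | 16.7 mL | 41.9 mL | – |
| Volume: threshold shifts 80 mL, capacity unchanged | 14% / 42% | 62.3 mL | 56.9 mL | 78.7 mL |
| Volume: threshold shifts 20 mL, capacity rises 40 mL | 14% / 10% | 21.9 mL | 21.5 mL | 19.2 mL |
| Pressure: amplitude cut by 90% in 40% of men, others unaffected | 3% / 37% | −4.1 cmH2O | −10.9 | −10.2 |
| Pressure: all amplitudes fall by 60% | 3% / 26% | −18.6 cmH2O | −17.8 | −17.0 |

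The first three rows and the sixth understate, at worst to 16.7 / 41.9 = 40% and 4.1 / 10.9 = 38% of the fuller analysis. The fifth and seventh overstate against the underlying effect: 21.9 / 19.2 = 1.14 and 18.6 / 17.0 = 1.09. In the fifth, fewer IDCs are lost on vibegron than on placebo. The fourth row understates against the underlying effect but exceeds the analysis with volume set to capacity, so even the sign depends on the target chosen.

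**The case against.** **The reported counts largely show the loss.** SAP 4.2.2 requires the number with available data in each continuous summary. In a UES table, change n gives the men with an IDC at both visits, Baseline n minus change n those who lost it, Week 12 n minus change n those who gained it, and the remainder those without one at either. This largely stands. It fails where an IDC trace was unreadable or the post-baseline test fell outside the Week 12 window of Days 57 to 113. The SAP's output list also assigns the urodynamics table to a set labelled SAF-UDS, although 7.6 says UES. Counts a reader must reconstruct do not repair the ANCOVA in any case.

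**The stakes are small.** This stands. The parameters are sub-study safety measures. SAP 3.1.7 names Qmax and PdetQmax as primary, and the IDC parameters have no margin, hypothesis or place in the testing hierarchy. Men who lose their IDC stay in the UES and in the analyses of capacity and maximum storage-phase pressure.

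**Setting a lost IDC to capacity is debatable.** This also stands. SAP 7.6 describes one volume as instilled and the other as corrected, and does not show that they share a scale. Capacity is also only a lower bound when no IDC occurs.

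**A stronger reading is tempting:** that the plan necessarily understates vibegron's effect, or discards its clearest response. The documents do not support it. They give no IDC rate, abolition rate or effect size, and some assumed scenarios overstate.

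**Conclusion.** The defect is real and narrow. Followed exactly, SAP 7.6 with 4.2.3 and 4.3.4 produces between-arm estimates for two parameters in men selected partly by their Week 12 outcome. Those estimates should not be read as randomised comparisons. This follows from the text, taking 7.6 at its word that the ANCOVA covers every parameter.

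The bias is probably toward understatement if vibegron abolishes IDCs more often than placebo does. Its direction and size cannot be established from the documents, and the figures above only illustrate assumed inputs. Qmax, PdetQmax, capacity, storage-phase pressure, the sub-study power and every co-primary and secondary endpoint are untouched. This is a cheap improvement, not a threat to the trial's conclusions.

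**What to change.** In SAP 7.6:
1. Tabulate IDC present, absent or not assessable at Baseline and Week 12 by arm, with the shift between visits.
2. Report the between-arm difference in Week 12 IDC presence among all UES men tested at Week 12. This keeps the men who lost their IDC.
3. Present both IDC parameters descriptively only, labelled as conditional on an IDC at both visits, with no ANCOVA treatment contrast.
4. Optionally, add a supportive volume analysis that treats no IDC as censored at capacity, or a rank-based one, after confirming that instilled volume and corrected capacity are on the same scale.

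The cost is SAP wording and one table from data already collected, and the loss of model-based estimates for the two parameters. The comparison in item 2 will be imprecise. Suppose 60% have a baseline IDC, 30% lose it on vibegron and 10% on placebo, and no new IDCs appear. Week 12 presence is then 0.6 × 0.7 = 42% against 0.6 × 0.9 = 54%, a difference of 12 points. With 30 men per arm, the 95% half-width is 1.96 × √(0.42 × 0.58 / 30 + 0.54 × 0.46 / 30) = 25 points. It should be reported as an estimate with its interval, not as a test.

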7.7. Uroflow Measures

Uroflowmetry is conducted at Screening and Week 24 (or early withdrawal). Measured parameters include maximum flow rate (Q_{max}) (mL/s), average flow rate (Q_{ave}) (mL/s), and volume voided (VV) (mL).

Uroflowmetry measures require a minimum void of 125 mL to be interpretable. Summary statistics will only be provided for uroflow tests where $VV \geq 125$ mL. The summary will comprise a continuous summary at baseline and post-baseline, including change from baseline. Least squares mean estimates and 95% CIs as described in section 4.2.2 will be presented from an ANCOVA model including terms for treatment and baseline parameter value.

If a uroflow measurement was taken after the end of study date in URO-901-3005 (implying that the subject initiated URO-901-3006 before the evaluation), that measurement will not be included in any tabular summaries but will be listed. All Uroflow measurements will be listed.

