5.2. Exclusion Criteria

At the **Visit 1 (Screening)** visit (and other timepoints as noted), a subject will not be eligible for inclusion in this study if any of the following criteria apply, unless otherwise noted:

1. Subject has a history of 24-hour urine volume greater than 3,000 mL or over 3,000 mL based on 3-day Bladder Diary at Visit 2 (Run-In) or Visit 3 (Baseline) visits.
2. Subject is a night-shift worker or plans to become a night-shift worker during the study.
3. Has lower urinary tract pathology that could, in the opinion of the investigator, be responsible for urgency, frequency, or incontinence; including, but not limited to, bladder stones, interstitial cystitis, prostate cancer, persistent urethral stricture, urogenital tuberculosis, and urothelial tumor.
4. Has a history of prostate surgery, including minimally invasive transurethral or transrectal procedures, procedural treatments for BPH within 6 months of Screening or has a planned prostate surgery, including minimally invasive prostate procedures, during the study period. Has a previous or planned pelvic radiation, low anterior resections (LAR), or any abdominoperineal resections (APR) during the study period.
5. Subject had prostatitis in the past 6 months.
6. Has a history of urinary retention requiring an intervention (eg, catheterization) for any reason.
7. Irregular use of long-acting medications (eg, tadalafil) to treat erectile dysfunction (ED). Note: ED medications with a short half-life such as sildenafil and vardenafil may be used on an irregular basis.
8. Subject has any planned procedures to treat ED (eg, implantation of a penile device) during the treatment period, or has any planned prostate procedure.
9. Subject is using any herbal medications to treat overactive bladder, lower urinary tract symptoms/BPH symptoms, or erectile dysfunction in the past 28 days prior to Screening.
10. Subject started using diuretics within 28 days prior to Screening. Subjects already taking any diuretics on stable doses for at least 28 days prior to Screening are allowed to enroll to the study.
11. Has maximum urinary flow (Qmax) < 5.0 mL/second with a minimum voided volume of 125 mL at Screening.
12. Has a history of or current nocturnal polyuria at Visit 2 (Run-In) or Visit 3 (Baseline) visits, based on 3-day Bladder Diary. Nocturnal polyuria is defined as more than one third of the total urine output per 24 hours occurring at night time.

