1.2.3.2. Statistical Hypotheses for Secondary Efficacy Endpoints

The secondary efficacy objectives of the study are to demonstrate that vibegron 75 mg is superior to placebo with respect to mean CFB to Week 12 in the following 4 endpoints. The null hypothesis is that there is no difference in mean CFB to Week 12 between vibegron 75 mg and placebo. The alternative hypothesis is that vibegron 75 mg is different (i.e., two-sided hypothesis) from placebo with respect to CFB to Week 12 in the following parameters, respectively. These tests will be performed sequentially each at an alpha level of 0.05 after the co-primary endpoints are tested and both demonstrate statistical superiority of vibegron 75 mg over placebo at a significance level of 0.05, see details described in section 4.1.2.

- Average number of nocturia episodes per night
- Average number of daily urge urinary incontinence episodes for subjects with urinary incontinence at baseline
- IPSS Storage score (1-week recall)
- Average volume voided per micturition

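### The 125 mL filter on uroflow tests selects on a post-randomisation outcome that vibegron may change, and the plan neither counts the removed tests by arm nor analyses them

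*SAP*

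**What the plan says.** SAP 7.7 sets the schedule: "Uroflowmetry is conducted at Screening and Week 24 (or early withdrawal"). Qmax, average flow and VV are measured. The reason for the filter is given as "Uroflowmetry measures require a minimum void of 125 mL to be interpretable", and the rule follows: "Summary statistics will only be provided for uroflow tests where" VV is 125 mL or more. What is then summarised is a "continuous summary at baseline and post-baseline, including change from baseline", with least squares means from an "ANCOVA model including terms for treatment and baseline parameter value". The filter therefore applies to the post-baseline test as well as to the baseline one, and the model has no voided-volume term.

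Tests below the threshold go only to a listing. SAP Table 9 names one uroflow table (14.3.8.1, safety set). SAP 4.2.3 adds: "In general, missing safety data will not be imputed and only observed values will be analyzed".

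Elsewhere, "Average volume voided per micturition" is the fourth secondary endpoint, tested for superiority (SAP 1.2.3.2 and 4.1.2). Protocol 5.2, criterion 11, uses the same volume at entry: Qmax below 5.0 mL/s excludes a man "with a minimum voided volume of 125 mL at Screening".

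**The concern.** Restricting an analysis by a characteristic fixed before randomisation leaves the arms comparable. Restricting it by something measured under treatment does not, if treatment can move that thing. Here the filtering variable is voided volume at the on-treatment test, and the plan's own efficacy hypothesis is that vibegron changes volume voided.

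Each man has essentially one post-baseline test, so a filtered test is not replaced by another visit. If a man's voiding deteriorates and his test void falls under 125 mL, he leaves the Qmax comparison and appears only in a listing. If the drug raises voided volume instead, more vibegron men pass the filter, and the two analysed groups differ for that reason.

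Uroflow is a named safety endpoint in a trial that the protocol justifies partly by the risk of urinary retention in men with BPH. A reader who sees similar Qmax means in the filtered table cannot tell preserved flow from selective removal. SAP 4.2.2 does show N and n for continuous summaries, but n does not separate a filtered test from one never done.

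**Working it through.** **No figure to reproduce.** SAP 7.7 states no sample size, margin, power or expected removal rate. I borrow one input, the Qmax SD of 3.2 mL/s from SAP 1.2.4.2 (urodynamics sub-study). The calculation it comes from reproduces: with 30 per arm, margin 3 mL/s and one-sided 0.05, power is Φ(3/(3.2·√(2/30)) − 1.645) = Φ(3.631 − 1.645) = 97.6%, against about 97% stated.

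**Assumptions (not in the documents).** Week 24 VV is normal with mean μ = 180, 220 or 260 mL and SD 80 mL. Qmax change has SD 3.2 mL/s and correlation ρ with VV. Let a = (125 − μ)/80 and λ(a) = φ(a)/(1 − Φ(a)). Then:
- share kept = 1 − Φ(a);
- mean Qmax change among kept tests = true change + 3.2·ρ·λ(a).

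These are raw differences, without the baseline covariate.

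**Case 1: the drug raises VV and has no effect on Qmax.** With μ = 180 and a rise of 20 mL:
- placebo: a = −0.6875, kept 75.4%, λ = 0.418;
- vibegron: a = −0.9375, kept 82.6%, λ = 0.311.

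The Qmax difference among kept tests is 3.2 × 0.3 × (0.311 − 0.418) = −0.10 mL/s at ρ = 0.3 and −0.17 at ρ = 0.5, when the truth is 0. Over all three means and rises of 20 to 40 mL, the share kept differs between arms by about 2 to 13 percentage points and the spurious difference is −0.04 to −0.31 mL/s, against vibegron. The uroflow VV summary is also truncated on its own value: a true 20 mL rise shows as 20 + 80 × (0.311 − 0.418) ≈ 11 mL.

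**Case 2: some vibegron men deteriorate.** Suppose 10% lose 5 mL/s, so the all-men effect is −0.50, with ρ = 0.4 (3.2 × 0.4 = 1.28). With μ = 180 and VV falling by 60 mL in those men:
- deteriorated men: a = 0.0625, kept 47.5%, λ = 0.838, mean change −5 + 1.28 × 0.838 = −3.93;
- other men: kept 75.4%, mean change 1.28 × 0.418 = 0.535;
- vibegron mean among kept = (0.9 × 0.754 × 0.535 − 0.1 × 0.475 × 3.93)/(0.9 × 0.754 + 0.1 × 0.475) = 0.243;
- difference = 0.243 − 0.535 = −0.29.

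| μ (mL) | VV fall 0 | VV fall 60 mL | VV fall 100 mL |
|---|---|---|---|
| 180 | −0.50 | −0.29 | −0.16 |
| 220 | −0.50 | −0.36 | −0.24 |
| 260 | −0.50 | −0.41 | −0.32 |

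With 5% deteriorating, the true −0.25 becomes −0.08 to −0.21 when VV falls by 60 to 100 mL. Between 29% and 83% of the deteriorated men are kept in those cells. With no fall in VV there is no attenuation.

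**A second model, with the ANCOVA, by simulation.** Assumptions: lognormal VV with mean 150 to 200 mL and CV 40 to 50%, between-visit correlation 0.5 on the log scale, Qmax = 6 + 0.03·VV plus a person effect (SD 3) and noise (SD 2). Then 15% to 44% of placebo tests fall below 125 mL.
- If 8% are impaired (VV halved, a further −4 mL/s), the all-men effect is about −0.5 to −0.6 and the filtered one about −0.05 to −0.2 mL/s.
- If VV does not fall in the impaired men, both are about −0.3.

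**The case against.** The strongest reply has four parts.

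1. **The threshold is a measurement rule, stated in advance and consistent with the entry criterion.** This stands. Low-volume Qmax is hard to interpret, and a small void may only reflect a poorly filled bladder. The filtered table should remain.

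2. **Voiding safety is measured elsewhere without this filter.** This stands in part. Post-void residual is summarised by visit with categories up to 300 mL or more, retention is an event of special interest, and IPSS is unfiltered. The sub-study gives urodynamic Qmax and pressure. These limit the harm. They do not repair the Qmax comparison: the sub-study has about 60 men, a retention event requires catheterisation, and residual volume and IPSS are not flow.

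3. **An unadjusted all-tests ANCOVA could mislead, because Qmax rises with volume.** In the second model a pure 20 mL rise gives 0.03 × 20 = +0.6 mL/s in all tests. That is correct, but it is the total effect in the randomised groups, and it should be labelled so. The filtered analysis is not free of the problem: it shows about +0.3 to +0.4. With harm and a 20 mL rise together, both analyses mask the harm; in the runs made, the all-tests result was about 0.0 to +0.1 and the filtered one about +0.1 to +0.25.

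4. **Men under 125 mL at Screening are selected before randomisation.** This stands. Their loss costs precision but does not break randomisation. The Part 1 schedule also has a second uroflow at Baseline, so a low Screening void need not remove a man.

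**Conclusion.** The point holds in a limited form. The post-baseline part of the filter selects on an outcome that treatment may change, and the plan has no by-arm accounting of what it removes and no analysis that includes the removed tests. It should be repaired in the SAP, and the repair is small.

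A reader might go further and infer that the filter leans the result toward no harm, or that every man whose voiding deteriorates drops out. The documents do not support that. A man leaves only if his test void is under 125 mL. Harm is attenuated only when impairment comes with such voids; it is not attenuated when volume is unchanged; and a rise in volume can push the filtered difference either way, as the two models show. Nor is the threshold itself the defect.

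The size cannot be read from the documents, which give no VV distribution. The eligibility limits (8 to 20 voids a day, at most 3,000 mL a day) give only ceilings on the average diary void, 3,000/8 = 375 mL down to 3,000/20 = 150 mL, and diary voids are not clinic uroflow voids. The figures above show what the filter could do under stated assumptions; they do not forecast this trial.

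**What to change.** Keep the VV ≥ 125 mL summary and ANCOVA in SAP 7.7 as the main uroflow analysis, and add two blocks.

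(a) By arm and visit: tests done, tests with VV under 125 mL, tests missing, and men unable to void where this is recorded. For the Week 24 or early-withdrawal test, give the between-arm difference in the proportion under 125 mL with a 95% CI.

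(b) The same ANCOVA on all recorded tests regardless of VV, as a supportive sensitivity analysis. Label it as the total effect on Qmax, including any effect that runs through voided volume.

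Report and discuss any discrepancy between the two analyses. A rule that a conclusion must hold in both is not needed, because SAP 7.7 sets no hypothesis or margin for uroflow.

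Cost: two table blocks from data already collected and listed. The drawback is that Qmax from small voids is noisier, so (b) is supportive only.
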